2.6.4 Laboratory data

[figure not shown]
Laboratory evaluation of NT-proBNP will be used for primary efficacy analysis as mentioned before. The remaining laboratory evaluations will not be entered in the eCRF, values will only be used locally to trigger adverse events as described in the protocol.

2.7 Protocol adherence

Medication adherence will be presented as the percentage of time on medication during the study follow-up, excluding any temporary or permanent interruptions due to adverse events or patient choice. The percentage of medication use will be described by mean and standard deviation. Additionally, the number of patients who required temporary or permanent discontinuation of the medication due to adverse events, medical decision, personal choice, or other reasons will be reported.

Moreover, this time will be broken down into mean exposure times to dosages 1, 2, and 3 for each group, similarly, to presented on Figure 2 below.

Figure 2. Titration of the treatment drug at each visit.

2.8 Exploratory analyses

The exploratory endpoints are:

1. Number of ventricular fibrillation or sustained ventricular tachycardia needing specific pharmacological, electrical or other treatment.
2. Number of anti-tachycardia pacing or shock therapies (In the subset of patients with an ICD or CRT-D at randomization)
3. Change of NT-proBNP at month 8.

Exploratory analyses will be performed on the FAS. There will be no formal inferential analyses. Descriptive summary statistics over time for baseline, actual value, and change from baseline will be presented for each treatment arm.

The number of sustained ventricular tachycardia events needing specific treatment or ICD implantation will be analyzed using a negative binomial model (McCullagh and Nelder 1989) with the count data as the dependent variable and treatment group and country as fixed-effect factors and log (follow-up duration) as the

off-set. The model estimated event rates (intensities/risk rate) and their 95% confidence intervals will be provided by treatment group. The treatment comparison will be performed through the estimated ratio of risk rates. The estimated risk ratio and its 95% confidence interval will also be provided. Note that, in case when the follow-up durations depend on the treatments (informative censorings), the estimated rate reduction should be interpreted with caution. However, when sacubitril/valsartan has a reduction in mortality, the rate ratio estimated from the negative binomial model will become conservative.

Change from baseline of NT-proBNP at month 8 will be analyzed similarly as the evaluation at week 12, using ANCOVA models.

The impact of the concomitant use of SGLT2Inhibitors in CV death and hospitalizations due to HF will be evaluated with proportional hazard Cox models using the interaction of the use of SGLT2 Inhibitors as time dependent covariate with the treatment arm in FAS and PPS subsets. Results will be presented in hazard ratios with 95% confidence intervals.

Troponin will also be summarized at baseline, month 8 and for change from baseline at month 8 as well as absolute change from baseline at month 8 by treatment group.

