1. To test whether sacubitril/valsartan is superior to enalapril in reducing ventricular fibrillation or sustained ventricular tachycardia needing specific pharmacological, electrical or other treatment	1. Number of ventricular fibrillation or sustained ventricular tachycardia needing specific pharmacological, electrical, or other treatment
2. In the subset of participants with an implantable cardioverter defibrillator (ICD) or CRT-D at randomization: to test whether sacubitril/valsartan is superior to enalapril in reducing anti-tachycardia pacing or shock therapies	2. Number of anti-tachycardia pacing or shock therapies

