## **4 Rationale**

### **4.1 Rationale for study design**

This study has a prospective, randomized, open-label blinded-endpoint adjudication (PROBE) design (Hansson et al 1992). Investigators and participants will have full knowledge of the treatment allocation but the independent Endpoint Adjudication Committee will be blinded to treatment allocation.

Blinded end-point evaluation of all of clinical events, which could potentially fulfill the criteria for the primary or secondary endpoints, will be assessed during the study and reported to an independent Clinical Endpoint Adjudication Committee for respective assessment and adjudication.

Blood samples will be obtained to determine changes from Baseline in NT-proBNP.

In order to minimize the potential impact of knowledge of study treatment, **no** aggregate statistical analyses performed during the study will include treatment assignment. The study Steering Committee and the study team from Novartis and the vendor ARO (the Brazilian Clinical Research Institute) will be blinded to the study treatment assignment and only the (DMC) will see data with treatment assignment during the study. The analyses for their safety monitoring meetings (which will occur every 6 months) will be performed by an independent statistician working with the DMC.

The slow Titration Period is similar to that of the conservative arm of the TITRATION study. Patients with CCC are at high risk of hypotension, and slow titration is necessary to ascertain tolerability to the target dosages of sacubitril/valsartan and enalapril, and to minimize the risk of SAEs and participant dropouts.

The 36-hour washout is required for participants in previous use of an ACEI and randomized to sacubitril/valsartan to minimize the risk of angioedema, which potentially increases with simultaneous inhibition of ACE and NEP.

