## **6.4 Treatment blinding**

Treatment will not be blinded to participants, Investigator staff, and persons performing the assessments. However, treatment will be blinded to the clinical trial team to avoid any bias during the study. Blinding of the DMC and the Clinical Endpoint Adjudication Committee are described in separate documents as outlined in [Section 10.2.2](#) and [Section 10.2.3](#).

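### The negative binomial model for exploratory endpoint 1 leaves out ventricular fibrillation and gives ICD implantation an undefined role, so its rate ratio does not estimate the listed endpoint

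*SAP*

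**What the plan says.** The endpoint is stated consistently. SAP 2.8 lists it as "Number of ventricular fibrillation or sustained ventricular tachycardia needing specific pharmacological, electrical or other treatment". Protocol Table 2-1 has the same definition, "Number of ventricular fibrillation or sustained ventricular tachycardia needing specific pharmacological, electrical, or other treatment", paired with the objective of "reducing ventricular fibrillation or sustained ventricular tachycardia needing specific pharmacological, electrical or other treatment". Protocol 8.3.7, the endpoint list in Protocol 12.6 and SAP Table 1 agree.

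The analysis text that follows the list in Protocol 12.6 and in SAP 2.8 specifies a different count: "The number of sustained ventricular tachycardia events needing specific treatment or ICD implantation will be analyzed using a negative binomial model". The model has treatment group and country as fixed effects and log follow-up duration as the offset. It is to yield event rates by arm and a ratio of rates with a 95% confidence interval.

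Both sections also say "There will be no formal inferential analyses" and provide descriptive summaries by arm. SAP section 3, which lists changes to protocol-specified analyses, does not mention this endpoint.

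**The concern.** An endpoint and the dependent variable of its model should name the same events. Here they differ in two ways. VF, the more immediately dangerous of the two arrhythmias, is in the endpoint but not in the modelled count. ICD implantation is in the modelled count but not in the endpoint.

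A programmer following SAP 2.8 literally would exclude VF and would then have to decide alone what to do with implantations. The resulting rate ratio and interval would probably be reported as the trial's answer on ventricular arrhythmia. Little else would stand beside it as a count of episodes across the whole trial population. Exploratory endpoint 2 is restricted to participants with an ICD or CRT-D at randomisation. The Holter sub-study enrolled 21 of about 400 planned participants (SAP 2.13.1.2).

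**Working it through.** The plan gives no figure to reproduce for this endpoint, and no sample size, alpha or event number bears on it. The check is a comparison of texts.

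**Step 1: the two definitions side by side**

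| Element | Listed endpoint (Protocol Table 2-1, 8.3.7, 12.6 list; SAP Table 1, 2.8 list) | Modelled count (Protocol 12.6 and SAP 2.8 analysis text) |
|---|---|---|
| Treated sustained VT | counted | counted |
| Treated VF | counted | not named |
| ICD implantation | not named | named, role unclear |

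**Step 2: the two readings of the ICD phrase**

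- Reading A: an implantation is one of the treatments that make a sustained VT episode count. It adds no new type of event, and it could be placed under the endpoint's electrical or other treatment.
- Reading B: an implantation is itself a counted event, with or without a VT episode behind it.

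The grammar allows both, and no other section settles the matter.

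**Step 3: what each definition scores for a single participant**

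| Participant | Listed endpoint | Model, reading A | Model, reading B |
|---|---|---|---|
| Two defibrillated VF episodes, no VT, no implant | 2 | 0 | 0 |
| One treated sustained VT episode, no implant | 1 | 1 | 1 |
| ICD implanted, no documented VF or sustained VT | 0 | 0 | 1 |

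The first row is wrong under both readings. The third row is wrong only under reading B.

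**Step 4: what the rate ratio would estimate**

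Let s be the share of qualifying episodes in the enalapril arm that are VF. Let R_VF and R_VT be the rate ratios for VF and for treated sustained VT. For pooled event rates:

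- listed endpoint: R = s × R_VF + (1 − s) × R_VT
- model under reading A: R = R_VT
- difference, endpoint minus model: s × (R_VF − R_VT)

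The point estimate therefore moves only if treatment affects VF and VT differently, and by at most s times that difference. Even with equal effects, the fraction s of qualifying episodes is lost and the interval would generally be wider. Under reading B the model estimates a mixture of R_VT and the rate ratio for implantations, weighted by their shares of the count.

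The documents give no value for s, for the rate ratios of the two arrhythmias or for the implantation rate, so none of these expressions can be evaluated.

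**The case against.** The strongest reply is that this is loose wording in an exploratory analysis without formal inference. Descriptive summaries by arm are planned, so VF would not be wholly unreported. Some severe VF would also surface in secondary endpoint 3 (sudden death or resuscitated sudden cardiac arrest), or in exploratory endpoint 2 for participants who have a device at randomisation. All of this is correct and limits the consequence. It does not make the model match its endpoint: none of those outputs is a rate ratio for treated VF or sustained VT in the full analysis set.

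Two stronger inferences are tempting, and the documents do not support them.

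- A reader might infer that the model certainly counts ICD implantations as events, so that decisions by unblinded physicians are added to an arrhythmia measure and a sizeable part of the count is not arrhythmia. This holds only under reading B, and reading A is at least as natural. Any percentage for it would need an assumed implantation rate, an assumed number of episodes, and the further assumption that no implant had a qualifying arrhythmia behind it.
- A reader might infer that the open-label design makes the modelled count biased where the listed endpoint is not. The trial is open label (Protocol 6.4: "Treatment will not be blinded to participants, Investigator staff, and persons performing the assessments"), and Protocol 4.1 describes blinded adjudication for events "which could potentially fulfill the criteria for the primary or secondary endpoints", without naming exploratory endpoints. But the listed endpoint itself requires that the episode needed treatment, so it already depends on decisions by unblinded staff. Reading B would extend that dependence; it would not create it.

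Nor is this a SAP departure from the protocol or a late redefinition. The same sentence stands in the protocol of 10 November 2021, and the SAP repeats it.

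**Conclusion.** The mismatch is real and needs no assumption to establish. Followed literally, the model omits VF under either reading of the sentence, and the role of ICD implantation is undefined. The rate ratio therefore does not estimate exploratory endpoint 1 as it is listed throughout both documents, and nothing elsewhere in either document repairs this.

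The numerical effect is unknown. It depends on the VF share, on whether treatment acts differently on VF and VT and, under reading B only, on how many implantations there are. The consequence is confined to an exploratory result: the primary win ratio, the secondary endpoints, the type I error rate and the power are unaffected. The point is worth correcting because the wording is wrong as it stands and the correction is almost free.

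**What to change.** In SAP 2.8, before the database is locked and treatment codes are released:

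1. Define the dependent variable as the number of episodes of VF or sustained VT needing specific pharmacological, electrical or other treatment, matching the endpoint list.
2. State that an ICD implantation is not itself a counted event. Report implantations after randomisation as a descriptive count by arm.
3. Add a line to SAP section 3 recording the difference from the analysis text in Protocol 12.6.

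The negative binomial model, covariates, offset and analysis set stay as they are. No new data should be needed, since the endpoint already calls for VF episodes to be counted. The cost is a sentence or two in SAP 2.8 and one line in section 3; a protocol amendment is not necessary. Settling this before unblinding also means that the event definition cannot be chosen with results in view.

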2.9 Subgroup analysis

Subgroup analysis will consider the following variables according to PARADIGM study: age (<65, ≥65 yr), sex, race, NYHA class (I or II, III or IV), estimated GFR (<60 ml/min/1.73m², ≥60 ml/min/1.73m²), diabetes, systolic blood pressure (by median), ejection fraction (by median and ≤35%, >35%), atrial fibrillation, hypertension, prior use of ACE inhibitor or ARB, prior use of mineralocorticoid receptor antagonist, prior use of beta-blockers, prior use of SGLT2i, prior hospitalization for heart failure, time since diagnosis of heart failure (≤1 yr, >1 to 5 yr, >5 yr), and comparing participants randomized before December 31st, 2021 (during the Covid-19 pandemic) and after.

The subgroup analyses for the primary endpoint (win ratio) will be conducted, with results presented within each subgroup in forest plots or table.

Each win ratio variable (CV death, Time to first HF hospitalization, and NT-proBNP measurement at Week 12) will be presented as additional information if any subgroup performed differently for the primary endpoint. In that case, subgroup effects will be tested including interaction parameters in the models used to report the marginal treatment effect previously described in section 2.6.2.

2.10 Interim analysis

There are no Interim Analyses planned for this study. However, Interim safety assessments are planned to be performed according to Data and Safety Monitoring Board (DSMB) charter by an independent statistician not involved in the study conduct. The DSMB will typically meet twice a year, or as deemed necessary. It is expected approximately 6 DSMB meetings in 36 months' study duration. No alpha adjustment will be made once there are no prespecified interruption rule for superiority nor safety.

To reduce bias, all study team members involved in data analysis will remain masked to the treatment codes and the results of the interim analysis until all monitoring decisions are made and the database is locked for final analysis.

2.11 Sample size calculation

An analysis of the 55 patients with Chagas' disease in the enalapril group in PARADIGM (Ramires et al 2018) showed an event rate of 20 events per 100 subject-years for CV death plus hospitalization due to HF. Similar event rates, for CV death plus hospitalization due to HF in CCC patients, has also been seen in the BENEFIT and SHIFT studies. Therefore, we assumed a rate of approximately 20 events per 100 subject-years for the CV event (composite of CV death and first HF hospitalization) for the enalapril group. Approximately 66% of the first CV events are HF hospitalizations. For the sample size calculation, we assumed a rate of 16 events per 100 subject-years for the sacubitril/valsartan group, which corresponds to an effect of 20%.

The sample size was determined based on a simulation study under the assumptions of:

- a one-sided type I error rate of 2.5%,
- a target power of 85%,
- a uniform accrual of 18 months,
- a study duration of 36 months, i.e. the individual follow-up times varied between 18 and 36 months,
- an annualized event rate of 0.16 for the composite of CV death or first HF hospitalization in the sacubitril/valsartan group, and an annualized event rate of 0.20 for the composite of CV death or first HF hospitalization in the enalapril group,
- a relative change of NT-proBNP between week 12 and baseline that is 25% lower in the sacubitril/valsartan group compared to the enalapril group

During the simulation study, a simulated trial was considered to show superiority of sacubitril/valsartan over enalapril when the win ratio was significantly larger than one based on the one-sided significance level of 2.5%, and the estimated hazard ratio of sacubitril/valsartan versus enalapril for time to first HF hospitalization was less than one, and the estimated hazard ratio of sacubitril/valsartan versus enalapril for CV death was less than one.

Based on these assumptions and criteria for superiority, a study with 900 patients results in the target power of 85%. Moreover, 302 participants with events for the composite of CV death or first HF hospitalization can be expected in the study.

As the primary hierarchical composite endpoint is evaluable as long as subject experience either a HF hospitalization, CV death, or have a NT-proBNP value measured at Week 12, the sample size calculation did not assume any loss of follow-up.

A blinded sample size re-estimation may occur if the event rate is lower than expected or the number of patients lost to follow up is higher than expected during the

study. A review will be done when 50% of patients have been enrolled. Otherwise, the study will continue until 302 participants have experienced a CV event and all patients have a minimum follow-up of 12 weeks.

2.12 Justification for strategy used in Estimand framework

2.12.1 Primary Estimand

Table 5. Justification for strategy used in Estimand framework

Intercurrent Event	Strategy	Clinical Justification
Treatment discontinuation	Treatment policy	Treatment discontinuation is included in the treatment conditions of interest.
Non-CV death	While Alive	Only data before non-CV death is considered. Death naturally ends the observation period, only the observed part before the non-CV death should be taken into consideration.
Concomitant use of SGLT2 Inhibitor	Treatment policy	Concomitant use of SGLT2 inhibitor is included in the treatment conditions of interest. Use of this concomitant medication will be observed in both arms and is a usual clinical practice.
Covid-19	Treatment policy	Covid-19 is included in the target population of interest.
Treatment crossover (Switch after observing endpoint)	Treatment policy	Treatment crossover is included in the treatment condition of interest (since the switch doesn't have the confounding effect on the observed endpoint)
Treatment crossover (Switch before observing endpoint)	Treatment policy	Treatment crossover is included in the treatment condition of interest

before observing endpoint)		
-------------------------------	--	--

2.12.2 Supplementary Estimand for primary endpoint

Table 6. Justification for strategy used in Estimand framework

Intercurrent event	Strategy	Clinical Justification
Treatment discontinuation	Treatment policy	Treatment discontinuation is included in the treatment conditions of interest.
Non-CV death	Composite strategy	No differentiation between CV and Non-CV death, consider any death as the endpoint. Non-CV death is included in the Estimand endpoint.
Concomitant use of SGLT2 Inhibitor	Treatment policy	Concomitant use of SGLT2 inhibitor is included in the treatment conditions of interest. Use of this concomitant medication will be observed in both arms and is a usual clinical practice.
Covid-19	Treatment policy	Covid-19 is included in the target population of interest.
Treatment crossover	While on treatment	The data is censored at the time of the switch and no imputation is performed for NTProBNP

2.13 Additional Assessments

Protocol version 2.0 added additional assessments to be reported as sub studies. Analyses of the sub studies will not be presented in the CSR.

2.13.1 Holter monitoring

2.13.1.1 Objectives

1. To estimate the prevalence of arrhythmias (i.e., premature ventricular contractions [PVC], non-sustained ventricular tachycardia [NSVT], ventricular tachycardia [VT]) in participants with CCC.

1.1 Endpoint to address the objective

1. Composite of reduction in PVC burden, sustained VT, and non-sustained VT episodes at Randomization and Month 8 (arrhythmia burden).
2. To evaluate the effect of sacubitril/valsartan versus enalapril on the arrhythmia burden from Randomization to Month 8

2.1 Endpoints to address the objective

1. Correlation of arrhythmia burden with biomarkers.
2. Correlation of arrhythmia burden with CV mortality
3. Incidence of associated safety events (AEs/SAEs)
4. Incidence of atrial arrhythmias

2.13.1.2 Substudy Sample size

The sample size was estimated based on data available in Table 2 of Diego et al (2018), which include the following parameters:

- PVC burden (PVC/hour)
- Sustained VT
- Non-sustained VT (NSVT)

It was estimated that approximately 400 participants were needed to have adequate 80% power for each parameter separately, acknowledging the limitation that in the reference source used for the calculations, the data were from the same group of 120 participants treated with angiotensin inhibition alone for 9 months followed by angiotensin-neprilysin inhibition for another 9 months.

However, it was only possible to enroll 21 patients to perform to Holter evaluation.

2.13.1.3 Statistical hypothesis, model, and method of analysis

Summary statistics by treatment arm will be estimated for PVC burden, sustained VT, and nonsustained VT.

Due to low enrollment in the sub-study, the primary endpoint, initially specified for analysis using generalized mixed linear models with study site as a random effect in the intercepts to account for hierarchical site effects, will now be compared using non-parametric Mann-Whitney tests.

The correlation between arrhythmia burden and biomarkers, mortality, related safety events, and atrial arrhythmia incidence (exploratory analysis) will be presented descriptively. If feasible, Cox proportional hazards models will be adjusted based on baseline Holter measures and treatment group interactions.

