#### **16.6.6 Sample-size**

The sample size is estimated based on data available in Table 2 of [de Diego et al \(2018\)](#), which include the following parameters:

- PVC burden (PVC/hour)
- Sustained VT
- Non-sustained VT (NSVT)

It is estimated that approximately 400 participants are needed in order to have adequate 80% power for each parameter separately, acknowledging the limitation that in the reference source used for the calculations ([de Diego et al 2018](#)), the data were from the same group of 120 participants treated with angiotensin inhibition alone for 9 months followed by angiotensin-neprilysin inhibition for another 9 months.

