2.13.2.3 Statistical hypothesis, model, and method of analysis

Summary statistics by treatment arm will be presented for each MRI measurement. Evaluations of all MRI measurement at 8-month will be performed adjusted for baseline values. The reduction of fibrosis and the improvement of cardiac structure after 8 months of treatment will be analyzed using generalized mixed linear models considering the hierarchical effect of study site and participant. Results will be graphically displayed in boxplots. Missing values will not be imputed; analyses will be performed on FAS populations, including only participants with available MRI data.

3 Change to protocol specified analyses

SAP second version includes the recurrent event as a key secondary endpoint, changed the number of days alive out of the hospital time definition changed to within 1 year from randomization, and the NT-ProBNP evaluation at month 8 was included as exploratory endpoint.

4 Appendix

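### With 21 of about 400 planned Holter participants, the SAP's Mann-Whitney tests have no baseline covariate, no stated estimate or interval, and no stated choice between change and Month 8 values

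*SAP*

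**What the plan says.** Protocol 16.6.6 states that "approximately 400 participants are needed in order to have adequate 80% power for each parameter separately", with the inputs taken from a published table on 120 patients treated in sequence with the two drug classes. SAP 2.13.1.2 repeats this and adds: "However, it was only possible to enroll 21 patients to perform to Holter evaluation".

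SAP 2.13.1.3 gives low enrolment as the reason for abandoning the generalised mixed model with a random site intercept. The primary endpoint "will now be compared using non-parametric Mann-Whitney tests". Summary statistics by arm are also planned. Correlations with biomarkers, mortality, safety events and atrial arrhythmia become descriptive. The section then adds: "If feasible, Cox proportional hazards models will be adjusted based on baseline Holter measures and treatment group interactions".

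SAP 2.13.1.1 words the endpoint as a composite of reductions in PVC burden, sustained VT and non-sustained VT, measured at Randomization and Month 8. Protocol Table 8-1 schedules a Holter at both times.

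For the MRI sub-study, which has the same two time points, SAP 2.13.2.3 says: "Evaluations of all MRI measurement at 8-month will be performed adjusted for baseline values".

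**The concern.** Replacing a parametric model with a rank test is a reasonable response to skewed data in a small sample, but it does not address a shortfall from about 400 to 21. A Mann-Whitney test delivers a p-value, and the SAP names nothing to go with it. At this size a non-significant result is close to certain for any effect of the order planned. Without an interval it could be read as absence of an antiarrhythmic effect. A significant result would probably overstate the effect.

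Two details add to this. The randomisation Holter is scheduled for every sub-study participant but is not named as a covariate, while the MRI section of the same SAP adjusts for baseline. And the variable to be ranked is left open: change or Month 8 value, and one composite score or three separate parameters. With 21 participants, those choices could alter the result if made after the data are seen.

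**Working it through.** **1. The planned 400.** It cannot be reproduced, because neither document gives an effect size, SD, event proportion, alpha or sidedness for the sub-study. I back-solved instead, assuming two-sided 5%, 80% power and 200 per arm:

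d = (1.960 + 0.842) × √(2/200) = 2.802 × 0.1 = 0.280.

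This returns 200 per arm by construction and does not verify the 400. If the three parameters have different effect sizes, 0.28 describes only the one that set the sample size.

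**2. Power at 21.** The split is not stated; I took 10 v 11 from the main trial's 1:1 allocation, with all 21 evaluable at Month 8 and normally distributed data.

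| Case | Power at d = 0.28 |
|---|---|
| Exact Mann-Whitney, 10 v 11 (40,000 simulations) | 7.9% |
| Same, if the 400 was sized for Mann-Whitney (d = 0.287) | 8.2% |
| Splits from 7/14 to 9/12 | 8.0% to 8.8% |
| t-test, two-sided 5% | 9.4% |
| Normal approximation or t-test, one-sided 5% | 14% to 15% |

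Mann-Whitney power at 10 v 11 is 77% at d = 1.3 and 81% at d = 1.4. About 80% power therefore needs roughly 1.4 SD, five times the back-solved effect (1.4 / 0.28 = 5).

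**3. What the baseline covariate gains.** Let ρ be the correlation between the randomisation and Month 8 values (assumed; not in the documents). With equal variances, the variance of the baseline-adjusted comparison is:
- relative to change scores: (1 − ρ²) / [2(1 − ρ)] = (1 + ρ)/2 = 0.65, 0.75, 0.85 at ρ = 0.3, 0.5, 0.7;
- relative to Month 8 values: 1 − ρ² = 0.91, 0.75, 0.51 at the same ρ.

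Both ratios are below 1 at every ρ shown, so the adjustment helps whichever variable the Mann-Whitney test was meant for.

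Simulation at this sample size, with rank ANCOVA on ranked Month 8 and ranked randomisation values, agrees. Its type I error is near 5%; that of the exact Mann-Whitney test is about 4%, which explains a little of the difference. At a 1 SD effect and ρ = 0.5, power is about 64%, against about 54% for Mann-Whitney on either variable. For a reduction on a skewed (lognormal) scale, the figures are about 64% for rank ANCOVA and about 30% for Mann-Whitney on change.

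At d = 0.28, however, adjustment lifts power only to about 10% to 12%. The gain is in precision; the sub-study remains unpowered.

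**4. Events for the conditional Cox models.** SAP 2.11 gives composite rates of 0.16 and 0.20 per year, with 66% of first events being HF hospitalisations. About 34% are then CV deaths as first event. Expected number = 21 × [1 − exp(−0.34 × rate × years)]:
- 1.5 years: 1.6 to 2.0
- 2.25 years (midpoint of the planned 18 to 36 months): 2.4 to 3.0
- 3 years: 3.2 to 3.9
- 5 years: 5.0 to 6.1

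These omit CV deaths after an HF hospitalisation and all non-CV deaths. The mortality for Chagas cardiomyopathy cited in Protocol 1.1 (30%, 44% and 56% at 1, 2 and 3 years) gives 21 × 0.30 = 6.3, 21 × 0.44 = 9.2 and 21 × 0.56 = 11.8 all-cause deaths.

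**The case against.** The SAP is open about the problem. The 21 stands beside the 80% power statement, so no reader would apply that power to the enrolled sample. The correlations have been made descriptive, and SAP 2.13 keeps sub-study results out of the CSR. Nothing in the plan turns a Holter p-value into a claim. All of this stands, and it is why the point is small.

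A reader might infer three stronger things that the documents do not support:

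- **That baseline is ignored.** The endpoint is worded as a reduction, so a test on change would already subtract the randomisation value. The mixed model in Protocol 16.6.5 named no baseline covariate either, so the replacement did not remove one. What can be said is that no covariate is used and the ranked variable is not stated.
- **That Cox interaction models are committed to on about three deaths.** They are conditional on feasibility, and the outcome is not named. Three is one derived value in a range of about 2 to 6 CV deaths as first event, and up to about 12 deaths from any cause. The fair remark is that feasible is not defined. Interaction terms would be weak even at 12 events.
- **That 8% is the sub-study's power.** It is conditional on a back-solved effect and an assumed alpha.

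It can also be said that rank ANCOVA instead of Mann-Whitney is a matter of taste at n = 21, since power at the back-solved effect hardly moves. That is right about power. It does not answer the missing estimate and interval, the undefined variable, or the precision gained from a measurement already scheduled.

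**Conclusion.** The point holds as a minor improvement to the analysis. The sub-study has about 5% of its planned size (21/400), and the replacement analysis names a test without an estimate, interval, covariate or defined variable. Power is about 8% if d is about 0.28 at two-sided 5%, with a 10 v 11 split and all 21 evaluable. No assumption examined lifts it above about 15%.

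Using the randomisation Holter as covariate cuts variance by 15% to 35% against change scores and by 9% to 49% against Month 8 values, at assumed correlations of 0.3 to 0.7. It cannot rescue the comparison. It makes the between-arm result as precise as the data allow, and the interval shows how little that is.

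The wording on the Cox models is a side note. The trial's primary and secondary conclusions are not affected.

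**What to change.** In SAP 2.13.1.3:

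1. Replace the Mann-Whitney comparison with a rank-based ANCOVA for each Holter parameter separately (PVC burden, sustained VT, non-sustained VT). Month 8 is the outcome and the randomisation Holter value the covariate, consistent with SAP 2.13.2.3 for MRI. This also settles which variable is ranked.
2. Report a between-arm estimate with 95% CI for each parameter. The adjusted mean-rank difference divided by the number analysed, plus 0.5, can be read as the probability that a participant in one arm has the lower burden.
3. Label these comparisons exploratory because the sub-study is not powered at 21, as SAP 2.6.3.4 already does for the adverse events of special interest.
4. Optionally, name the outcome and a minimum event count for the Cox models, or omit them.

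The cost is a few sentences and one small model, with no new data. Sustained VT may be zero for most participants. Tied ranks would then carry little information, and the counts by arm should be shown beside the estimate. Participants lacking either Holter drop out of the adjusted analysis, so the number analysed should be stated.
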